3.9.3 Criteria for discontinuation of investigational product during the second year extension period:

Criteria for discontinuing investigational product at Week 52:

Subjects not meeting the criteria to continue in the second year extension will not receive any IP at Week 52 and will complete the study after completing the required follow-up visits.

Subjects meeting the following criteria may continue to receive blinded IP between Weeks 52 and 100.

- (i) Meeting all of the following criteria based on the renal portion of the PRR definition:
 - eGFR is:
 - ≥ 60 mL/min/1.73 m² or no confirmed decrease of eGFR from baseline of $\geq 20\%$
 - Improvement in 24-hour UPCR:
 - For subjects with a baseline UPCR ≤ 3 mg/mg: <1.0 mg/mg
 - For subjects with a baseline UPCR >3 mg/mg: $>50\%$ improvement from baseline and ≤ 3.0 mg/mg

Renal discontinuation criteria must be confirmed in two separate samples. The second measurement should be at least 1 week after the first measurement.

- (ii) No discontinuation of IP
- (iii) Negative HIV test after signing the Main ICF

Criteria for discontinuing investigational product at Week 52, Week 56 or Week 60

- Failure to obtain Pap smear after Week 48 with result available at Week 60 at latest
- Pap smear result not meeting the eligibility criteria (see [Appendix K](#)) at Week 52, 56, or 60 of a Pap smear obtained after Week 48
- Failure to obtain Week 52 QuantiFERON test result by Week 56

Criteria for discontinuing investigational product at Week 60 and later

- OCS >7.5 mg/day (except one OCS burst and taper)
- MMF >2 gm/day or >Week 52 dose, if Week 52 dose <2 gm/day

Subjects who discontinue the IP during the second year extension period will be followed until Week 104 (or for a minimum of 12 weeks after last dose of IP for subjects for whom IP was discontinued within 12 weeks of Week 104).

3.9.4 Criteria for discontinuation of investigational product for reasons other than lack of efficacy at any time during the study

Subjects may be discontinued from IP in the following situations:

1. Subject decision: The subject is at any time free to discontinue treatment, without prejudice to further treatment. The primary reason should be documented as one of the following:
 - (a) Subject is unable to comply with protocol-specified visits and/or procedures due to conflicts not related to clinical study
 - (b) An AE or laboratory abnormality is of concern to the subject, but not clinically significant to physician

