 - u This will be in addition to the central laboratory urinalysis. This will include urine sediment examination for red blood cells (RBC), white blood cells (WBC), and cellular casts (WBC, RBC and mixed) and hematuria on a dipstick test.
 - v Randomised subjects who receive anti-malarial therapy within 12 months prior to signing the ICF must have an eye exam by a qualified professional either within 12 months prior to signing the ICF or subjects who start on anti-malarial therapy during the Screening Period within 12 weeks after signing ICF.
 - w Check accountability and dispense Sponsor-provided MMF.
- 1 All Week 52 laboratory samples (blood and urine, including 24-hour UPCR sample) should be collected between Week 50 to Week 52, to allow assessment of PRR requirement for the second year participation.
 - 2 IP infusion at Week 52 is only for subjects who are continuing in second year extension period.

Table 3 Study plan detailing the procedures during follow-up (for subjects not participating in the second year extension period)

Study Period	Follow-Up Period	
	393±7 (8 weeks post final dose)	421±7 (12 weeks post final dose)
Days		
Visit Number	15 (Week 56)	16 (Week 60)
PtGA		X
C-SSRS (V1-V16)	X	X
PHQ-8		X
Vital signs	X	X
Tuberculosis Questionnaire	X	X
Physical examination	X	X
Weight	X	X
Blood collection for:		
Serum chemistry/haematology	X	X
Lupus serology tests (C3, C4, anti-ds DNA)	X	X
Type I IFN signature with 21-gene assay (PD marker)		X
RNA transcript profiling		X
ADA	X	X
PK blood samples ^a	X	X
Serum and plasma biomarkers		X
QFT-G test (TB testing), if applicable ^b		X

Study Period	Follow-Up Period	
Days	393±7 (8 weeks post final dose)	421±7 (12 weeks post final dose)
Visit Number	15 (Week 56)	16 (Week 60)
Urine collection for:		
Spot UPCR	X	X
Urinalysis (including microscopic examination) ^c	X	X
Local urinalysis (including microscopic examination) for selected sites ^d	X	X
Urinary biomarkers	X	X
Urine pregnancy tests (using dipstick)	X	X
eGFR using MDRD formula	X	X
SLEDAI-2K	X	X
PGA	X	X
AEs/SAEs/AESIs	X	X
SLEDAI-2K based Flare Assessment Instrument	X	X
Concomitant medications	X	X
Sponsor-provided MMF ^e	X	
Second renal biopsy (optional) ^f		X
Local clinical evaluation		X
Adjudication (optional)		X
Tissue biomarker ^g (optional)		X

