4.2.1.1 Assessment criteria for participation in the second year extension period (Week 52)

The 24-hour UPCR sample collected between Week 50 to Week 52 for the Week 52 response assessment will be used to assess criteria for participation in the second year extension period. The eGFR measured between Week 50 and Week 52 will be used to assess eligibility for participation in the second year extension period.

4.2.1.2 Initiation of dosing in the second year extension period (Week 52 to Week 60)

All efficacy and safety assessments for Week 52 must be completed prior to initiation of dosing in the second year extension period. The first dose in the second year extension period must be administered between Week 52 (+14 days) and Week 60. Prior to administering the first dose in the second year extension period, the Principal Investigator must confirm that all Week 52 safety assessments (including the ECG) are performed and that subject does not meet any withdrawal criteria. The Week 52 QFT-G test results must be available prior to Week 56 and results of the Pap smear must be found to meet eligibility requirements as described in [Appendix K](#) and available by Week 60 or IP administration will be discontinued.

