Subjects who exceed the maximum daily OCS dose at the Week 12 or Week 24 visits may continue to receive IP if the current dose is part of a temporary increase in OCS dose (e.g., protocol-allowed burst and taper). Subjects who cannot be returned to their pre-increase dose within 14 days from the start of increase will have their IP discontinued at the next visit.

Criteria for discontinuing IP at Week 52:

Subjects not meeting the criteria to continue for the second year extension period will not receive any IP at Week 52 and will complete the study after completing the required follow-up visits.

Subjects meeting the following criteria may continue to receive blinded IP between Weeks 52 and 100.

- (i) Meeting all of the following criteria based on the renal portion of the PRR definition:
 - eGFR is:
 - ≥ 60 mL/min/1.73 m² or no confirmed decrease of eGFR from baseline of $\geq 20\%$
 - Improvement in 24-hour UPCR:
 - For subjects with a baseline UPCR ≤ 3 mg/mg: <1.0 mg/mg
 - For subjects with a baseline UPCR >3 mg/mg: $>50\%$ improvement from baseline and ≤ 3.0 mg/mg

Renal discontinuation criteria must be confirmed in two separate samples. The second measurement should be at least 1 week after the first measurement.

- (ii) No discontinuation of IP.
- (iii) Negative HIV test after signed the Main ICF

Criteria for discontinuing IP at Week 52, Week 56 or Week 60:

- Failure to obtain Pap smear after Week 48 with result available at Week 60 at latest

- Pap smear result not meeting the eligibility criteria (see Appendix K of the Protocol) at Week 52, 56, or 60 of a Pap smear obtained after Week 48
- Failure to obtain Week 52 QuantiFERON test result by Week 56

Criteria for discontinuing IP at Week 60 and later:

- OCS >7.5 mg/day (except one OCS burst and taper)
- MMF >2 gm/day or >Week 52 dose, if Week 52 dose <2 gm/day

Subjects who discontinue the IP during the second year extension period will be followed until Week 104 (or for a minimum of 12 weeks after last dose of IP for subjects for whom IP was discontinued within 12 weeks of Week 104).

Criteria for discontinuation of IP for reasons other than lack of efficacy at any time during the study:

1. Subject decision: The subject is at any time free to discontinue treatment, without prejudice to further treatment. The primary reason should be documented as one of the following:

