4 ANALYSIS METHODS

4.1 General principles

4.1.1 Visit windows

For visit based analyses, the variables will be summarised based on the scheduled days with adjusted analysis-defined visit windows. The adjusted analysis-defined windows are summarised below:

Table 2 Visit windows

Adjusted Defined Windows Visit	Scheduled Study Day	Maximum Windows
Day 1	1	Study Day 1
Week 4	29	$2 \leq \text{Study Day} \leq 42$
Week 8	57	$43 \leq \text{Study Day} \leq 70$
Week 12	85	$71 \leq \text{Study Day} \leq 98$
Week 16	113	$99 \leq \text{Study Day} \leq 126$
Week 20	141	$127 \leq \text{Study Day} \leq 154$
Week 24	169	$155 \leq \text{Study Day} \leq 182$
Week 28	197	$183 \leq \text{Study Day} \leq 210$

Adjusted Defined Windows Visit	Scheduled Study Day	Maximum Windows
Week 32	225	211 ≤ Study Day ≤ 238
Week 36	253	239 ≤ Study Day ≤ 266
Week 40	281	267 ≤ Study Day ≤ 294
Week 44	309	295 ≤ Study Day ≤ 322
Week 48	337	323 ≤ Study Day ≤ 350
Week 52	365	351 ≤ Study Day ≤ 378
Week 56	393	379 ≤ Study Day ≤ 406
Week 60	421	407 ≤ Study Day ≤ 434
Week 64	449	435 ≤ Study Day ≤ 462
Week 68	477	463 ≤ Study Day ≤ 490
Week 72	505	491 ≤ Study Day ≤ 518
Week 76	533	519 ≤ Study Day ≤ 546
Week 80	561	547 ≤ Study Day ≤ 574
Week 84	589	575 ≤ Study Day ≤ 602
Week 88	617	603 ≤ Study Day ≤ 630
Week 92	645	631 ≤ Study Day ≤ 658
Week 96	673	659 ≤ Study Day ≤ 686
Week 100	701	687 ≤ Study Day ≤ 714
Week 104	729	715 ≤ Study Day ≤ 742
Week 108	756	743 ≤ Study Day ≤ 770
Week 112	784	771 ≤ Study Day ≤ 798

For assignment of data to time points using the visit windows, study day will be defined as (Date of assessment – date of first administration of IP) +1. Using this definition, the day of first dose of IP will be Day 1 and the scheduled visit date of Week 4 will be study day 29 (=28+1) for example.

If multiple readings are recorded within a single visit window, the following rules will be followed.

- If there are two or more observations within the same visit window, then the non-missing one closest to the scheduled visit will be used in the analysis.
- If two observations are equidistant from the scheduled visit, then the non-missing observation with the earlier collection date will be used in the analysis.
- If two observations are collected on the same day, then the non-missing one with the earlier collection time will be included in the analysis.

[figure not shown]
If a visit window does not contain any observations, then the data will remain missing.

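### At Week 52 only a failing renal result calls for a second 24-hour UPCR, and the closest-to-Day-365 rule can put that retest in place of the failing value, slightly flattering both arms

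*SAP*

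**What the plan says.** **When the Week 52 sample is taken.** Protocol Table 2, footnote 1: "All Week 52 laboratory samples (blood and urine, including 24-hour UPCR sample) should be collected between Week 50 to Week 52". That is nominally Day 351 to Day 365. Protocol 4.2.1.1 uses the same collection for the extension decision: "The 24-hour UPCR sample collected between Week 50 to Week 52 for the Week 52 response assessment will be used".

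**When a second sample is taken.** To continue on blinded product after Week 52 a subject must qualify by "Meeting all of the following criteria based on the renal portion of the PRR definition" (Protocol 3.9.3). For 24-hour UPCR that means below 1.0 mg/mg if baseline was 3 or less, or more than 50% improvement and no more than 3.0 if baseline was above 3. Failure has to be verified: "Renal discontinuation criteria must be confirmed in two separate samples. The second measurement should be at least 1 week after the first measurement". SAP 1.2.5 repeats the requirement: "Renal discontinuation criteria must be confirmed in two separate samples". Nothing asks for a second sample after a pass.

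**Which value is analysed.** The Week 52 window in SAP 4.1.1, Table 2, is "351 ≤ Study Day ≤ 378", with target Day 365. If it holds more than one observation, "the non-missing one closest to the scheduled visit will be used in the analysis". For ties: "If two observations are equidistant from the scheduled visit, then the non-missing observation with the earlier collection date will be used in the analysis". The section does not mention confirmatory repeats.

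**What reaches the endpoints.** Under SAP 4.1.3 and 4.2.1, subjects infused in the Week 48 window keep their Week 52 data. The selected value therefore enters the primary UPCR model and the UPCR component of CRR.

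**The concern.** Whether a confirmatory sample exists depends on the first result. A subject whose UPCR is high partly by chance fails, is sampled again and tends to be lower the second time. A subject whose UPCR is low by chance passes and keeps that value. If the retest then becomes the analysed value, the correction runs in one direction only.

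The quantities exposed are the Week 52 arm means of UPCR and the CRR rates. Both are planned outputs and natural inputs to later trial planning. More placebo than anifrolumab subjects would fail, so one should also check whether the treatment contrast moves.

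**Working it through.** **1. The plan's own figure.** Inputs from SAP 1.3: log SD of change 0.8, 100 versus 50 subjects, Week 52/baseline ratios 0.35 and 0.54, two-sided alpha 0.0499.
- SE = 0.8 × √(1/100 + 1/50) = 0.1386.
- ln(0.54/0.35) = 0.434, and 0.434/0.1386 = 3.13.
- Power = Φ(3.13 − 1.96) = 0.879, or 0.875 with the t distribution. The stated value is about 87%.
- The interval around 0.65 is 0.495–0.853 (stated 0.50–0.85). The minimal detectable ratio is 0.762 (stated 0.76).

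The design inputs reproduce and are used below.

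**2. When the retest displaces the first value.** Put the first sample k days before Day 365 (k = 0 to 14) and the retest g days later. The retest lies |g − k| days from Day 365, so it is strictly closer only if g < 2k. At g = 2k the tie rule keeps the first sample. The Day 378 limit never binds, because with k ≤ 14 any g < 2k gives a retest by Day 378.

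| Gap g (days) | First-sample days displaced | Of 15 possible days |
|---|---|---|
| 7 (minimum) | 351–361 | 11 |
| 10 | 351–359 | 9 |
| 14 | 351–357 | 7 |
| 21 | 351–354 | 4 |
| 28 or more | none | 0 |

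A first sample on Day 362–365 is always kept. If first-sample days were spread evenly and gaps were 10–14 days, replacement would occur in (9+9+8+8+7)/75 = 41/75, or 55%, of failures.

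**3. Why CRR is less exposed than it looks.** The retest is triggered by the PRR-based cut-offs, not by CRR's 0.7 mg/mg. A UPCR failure with baseline of 3 or less has UPCR of at least 1.0, so the retest must drop by ln(1.0/0.7) = 0.36 on the log scale to reach CRR. With baseline above 3 the failing value is above 1.5, and the drop needed is more than ln(1.5/0.7) = 0.76.

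**4. Size, by simulation.** One million subjects per arm, with the SAP's ratios and SD of change. Assumptions not in the documents: within-subject log SD of one 24-hour UPCR 0.1–0.4; baseline median 2.5 or 3.5 mg/mg, log SD 0.6, truncated above 1. eGFR, dropout and medication rules are ignored. Replacing every failing value (baseline median 2.5) gives, as anifrolumab / placebo:

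| Within-subject SD | CRR, first sample | CRR, retest used | Fall in geometric mean |
|---|---|---|---|
| 0.1 | 37.9% / 22.1% | 37.9% / 22.1% | 0.4% / 0.5% |
| 0.2 | 37.5% / 21.6% | 37.8% / 22.0% | 1.7% / 1.9% |
| 0.3 | 36.9% / 20.8% | 38.2% / 22.1% | 3.9% / 4.3% |
| 0.4 | 35.9% / 19.5% | 38.6% / 22.1% | 6.9% / 7.7% |

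Across all scenarios:
- About 31–36% (anifrolumab) and 52–57% (placebo) fail the PRR UPCR criteria. At most 8.9% and 5.0% of those failures fall to 0.7 or below on retest.
- Another 25–39% of subjects miss CRR without triggering any retest.
- The largest move in the between-arm ratio is from 0.649 to 0.655. The CRR difference changes by at most 0.3 points and primary power by at most 0.2 points.

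**5. Partial replacement.** With 55% replaced (step 2), baseline median 3 and SD 0.2–0.4, geometric means fall about 1–4% and CRR rises about 0.2–1.2 points. Runs with 47% replaced (a 14-day gap) agree: CRR rises 0.1–1.3 points.

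**The case against.** **Replacement is not automatic.** A reader might infer that the rule always, or usually, swaps in the retest. The documents do not support that. Seven days is the minimum gap, and a retest has to wait for the first result; the protocol quotes central-laboratory turn-around of up to 7 days for the stratification sample. Collection is preferred on the day before the visit, which for an on-time visit puts the first sample where it cannot be displaced. On the other side, Protocol 4.2.1 permits sampling up to 14 days early so that results are in hand for the extension decision, and that favours displacement. The timing distribution is unknown, so both partial and full replacement are shown.

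**Failures are not the only subjects resampled.** Protocol 5.1 lets any subject repeat a collection spoiled by infection, menstruation or poor technique. That stands, but such repeats depend on validity and not on the result.

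**No direct conflict with Protocol 4.2.1.1.** One might read that section as naming the first sample. It refers to a sample collected in Week 50–52 without saying which. With a first sample on Day 351–358 and a 7-day gap, the retest is itself a Week 50–52 sample.

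**The treatment comparison is essentially untouched.** This stands. The primary and secondary objectives are between-arm, and the simulation shows no material movement in either contrast.

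**A first-sample rule must not reach eGFR.** This also stands. CRR (SAP 3.2.1) counts a fall in eGFR only if it is confirmed, so a confirmatory eGFR is part of the endpoint.

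**Conclusion.** The point holds in limited form. The written rules allow the Week 52 UPCR value to be selected according to its own result, and the selection can only be triggered by a failing result. The effect is a small improvement in reported UPCR and CRR in both arms: about 1–4% and 0.2–1.2 points under partial replacement, and at most about 8% and 2.7 points if every failing value were replaced. These sizes rest on an assumed within-subject log SD of 0.2–0.4, on assumed baseline distributions and on assumed sampling times. At SD 0.1 the effect on CRR vanishes.

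A reader might go further and infer a biased treatment effect or a large distortion of CRR rates. Neither is supported: the ratio stays at about 0.65, the CRR difference moves by no more than 0.3 points, and most subjects who narrowly miss 0.7 are never retested. This is a minor improvement to the plan, not a threat to its conclusions.

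**What to change.** Add to SAP 4.1.1:
- The Week 52 24-hour UPCR is the first valid sample in the Week 52 window (Day 351–378). Late but legitimate samples are therefore kept.
- A collection judged invalid under Protocol 5.1 is replaced by its repeat.
- A UPCR sample taken only to confirm failure of the extension criteria serves the extension decision and does not supply the Week 52 endpoint value.
- The rule does not apply to confirmatory eGFR, which stays available for the confirmed-decrease component of CRR.
- The closest-to-Day-365 choice is reported as a sensitivity analysis for UPCR and CRR.

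The cost is a few sentences and one extra analysis run. No new data are needed, no subject loses a Week 52 value, and the extension criteria are unchanged.

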3.7 Methods for unblinding

The treatment code should not be broken except in medical emergencies when the appropriate management of the subject requires knowledge of the treatment randomisation. The

Investigator must document and report the action to AstraZeneca or designee, without revealing the treatment given to subject to the AstraZeneca staff or the designee. Instructions for unblinding an individual subject's IP allocation are contained in the IXRS manual. In general, unblinding should only occur if management of the medical emergency would be different based on the subject having received IP. In the majority of cases, the management of a medical emergency would be the same whether or not IP was received by the subject. If this was the case, the IP allocation should not be unblinded. Subjects who have been unblinded by the Investigator must be discontinued from IP.

One interim analysis may be conducted after approximately 50% of subjects have completed the Week 52 visit. CCI [REDACTED]

CCI [REDACTED]

[REDACTED] Details of the interim analysis including a description of who will be unblinded will be specified in the interim analysis and communication plans prior to unblinding.

After all randomised subjects have completed the 52 week double-blind period the data base will be soft-locked, and the **primary analysis** will be performed, including the assessment of the primary, secondary, and safety objectives. This analysis will also encompass available data collected after the 52 week time point and details will be provided in the SAP. At this stage the Sponsor and Sponsor's delegate who are not directly involved in the management of sites will be unblinded to randomised treatment, but the subjects and investigators will remain blinded (single-blind). The **end of study analysis** will be performed after all subjects have completed the second year extension period.

AstraZeneca or its designee retains the right to break the code for SAEs that are unexpected and are suspected to be causally related to an IP and that potentially require expedited reporting to regulatory authorities. Treatment codes will not be broken for the planned analyses of data until all decisions on the evaluability of the data from each individual subject have been made and documented.

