- Weeks 12, 24, 36, 52, 64, 76, 88, and 104: Within 2 weeks of the actual date of visit when the collection was due and if applicable, before any change in SOC or concomitant medications is made (Week 52 sample must be collected before second year extension period dosing)

The 24-hour UPCR will be used only for the primary and secondary endpoints, the PRR, aCRR, graded CRR, and graded aCRR criteria at Week 52 and Week 104, the 24-hour UPCR and CRR at Week 104 and to determine withdrawal criteria at Weeks 12, 24 and 52.

- **Spot UPCR:** Spot UPCR will be performed at all visits and will be used for the calculation of SLEDAI-2K and for the CRR and PRR classification, when evaluating time to achieve renal response modified to include OCS tapering requirement as well as for the CRR and PRR

classification for flare assessments. All assessments except as noted above for the 24-hour UPCR will be based on the spot UPCR. The change in proteinuria will also be assessed based on spot UPCR at Weeks 24, 52 and 104. The spot UPCR sample should be taken prior to administration of IP, on a clean catch urine sampling. The same urine sample can be used for spot UPCR and sediment analysis.

- Urine sediment examination will be performed at all visits: Selected sites will perform local urinalysis including a microscopic examination. The microscopic examination must be assessed by trained personnel, and can be assessed by the site or a local laboratory. This data will be used for exploratory analyses. This will be in addition to the central laboratory urinalysis.
- Estimated glomerular filtration rate based on the MDRD formula calculated by the central laboratory. Refer to the Laboratory Manual for specifics.

The efficacy assessments based on clinical evaluation include SLEDAI-2K (Section 5.1.2, Appendix F), PGA (Section 5.1.4), OCS reduction (Section 5.1.5), and SDI (Section 5.1.3). The assessments for quality of life and patient-reported outcomes are summarised in Section 5.3.1.

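### A protocol-compliant Week 52 repeat of the 24-hour UPCR can fall as late as Day 386, but the SAP's date-only Week 52 window closes on Day 378

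*SAP*

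**What the plan says.** **Protocol.** Section 5.1 covers a 24-hour UPCR whose validity is affected by a medical reason, or which was not properly collected. At Weeks 12, 24, 36, 52, 64, 76, 88 and 104 it may be done or repeated "Within 2 weeks of the actual date of visit when the collection was due". The repeat must come before any change in background or concomitant treatment and, at Week 52, before extension dosing. Protocol Table 2 gives each of these visits a window of ±7 days. Its footnote 1 says that Week 52 laboratory samples "should be collected between Week 50 to Week 52". Section 4.2.1.2 adds: "The first dose in the second year extension period must be administered between Week 52 (+14 days) and Week 60".

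**SAP.** Section 4.1.1 assigns each result to a visit by its study day. Table 2 defines Week 52 (scheduled Day 365) as "351 ≤ Study Day ≤ 378", and Week 56 starts on Day 379. If one window holds several results, "the non-missing one closest to the scheduled visit will be used in the analysis", and a tie goes to the earlier date. For an empty window: "If a visit window does not contain any observations, then the data will remain missing".

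Three other SAP passages come close but do not settle the matter:
- Section 3 deals with an invalid value at baseline only.
- Section 3.3.16 ties an assessment to its nominal visit for PGA only.
- The end of Section 4.1.1 mentions repeats only for analyses not based on a particular visit.

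**The concern.** Two current rules for the primary-endpoint sample do not meet. A site can follow Protocol 5.1 exactly and obtain a valid Week 52 replacement, which the SAP then files under Week 56. No 24-hour UPCR is scheduled there, and the primary MMRM in SAP 4.2.1 uses data from baseline to Week 52, so the value is lost to the primary analysis.

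For CRR, the missing component goes to the carry-forward and non-responder rules in SAP 4.1.4.2 and 4.1.4.3. If only scheduled 24-hour UPCR visits count, the Week 36 value would be carried forward when there is one. If every four-weekly visit counts, Week 52 is not the first missing visit and the subject becomes a non-responder. Either way an imputed outcome replaces a valid measurement.

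At Weeks 12, 24 and 36 a late repeat moves to Week 16, 28 or 40. Read literally, fitting all data up to Week 52 would then add sparse visit levels to a model with unstructured covariance.

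A second, conditional point concerns two results inside one window. If a flawed first result stays in the data, the closest-day rule can prefer it to the valid repeat.

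**Working it through.** **1. Reproduce the SAP window.** Scheduled day = 7 × week + 1, so Week 52 is Day 365. Window limits are the midpoints between neighbouring scheduled days, with the midpoint given to the later visit. (337 + 365)/2 = 351 and (365 + 393)/2 = 379, so Week 52 runs from Day 351 to Day 378, as in SAP Table 2.

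**2. Latest compliant repeat.** Scheduled day + 7 (visit window) + 14 (repeat allowance). The SAP window ends at scheduled day + 13.

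| Week | Scheduled day | Latest compliant day | SAP window ends | Overrun (days) |
|---|---|---|---|---|
| 12 | 85 | 106 | 98 | 8 |
| 24 | 169 | 190 | 182 | 8 |
| 36 | 253 | 274 | 266 | 8 |
| 52 | 365 | 386 | 378 | 8 |
| 64 | 449 | 470 | 462 | 8 |
| 76 | 533 | 554 | 546 | 8 |
| 88 | 617 | 638 | 630 | 8 |
| 104 | 729 | 750 | 742 | 8 |

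**3. When it can happen at Week 52.** For an actual visit on Day v, the number of the 14 post-visit repeat days that miss the window is max(0, v + 14 − 378). This gives 0 for visits on Days 358 to 364, 1 on Day 365, 4 on Day 368 and 8 on Day 372. These are counts of calendar days, not expected frequencies. They also ignore the requirement that the repeat precede treatment changes and extension dosing.

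**4. Conditional selection within the window.** Take a first sample on Day 365 − k and a repeat on Day 365 + j. The first is kept if j ≥ k.
- First sample on Day 365 (k = 0): every repeat on Days 366 to 378 loses to it.
- First sample on Day 358 (k = 7): repeats from Day 372 lose.
- First sample on Day 351 (k = 14): the tie would fall on Day 379, outside the window, so no in-window repeat loses.

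**5. Effect on power.** From SAP 1.3: ratios 0.54 and 0.35, SD 0.8, two-sided alpha 0.0499, 100 pooled against 50 placebo. Difference = ln(0.54/0.35) = 0.4336. SE = 0.8 × √(1/100 + 1/50) = 0.1386. Power = Φ(0.4336/0.1386 − 1.961) = 87.9%, against the SAP's approximate 87%. The same formula with Week 52 values lost, and no credit for earlier visits in the MMRM, gives:
- one pooled-arm value lost (99/50): 87.8%
- one placebo value lost (100/49): 87.4%
- 2% lost in each arm (98/49): 87.2%
- 5% lost in each arm (95/47.5): 86.2%

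The documents do not give the share of subjects needing a repeat, so 2% and 5% are assumptions.

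**The case against.** **It is a corner case.** Week 52 samples are directed to Weeks 50 to 52, the SAP window opens on Day 351 to match, and it leaves 13 days after Day 365. Day 386 needs the latest visit and the latest repeat together. Protocol Table 2 places extension IP at the Week 52 visit itself, so a continuing subject dosed then cannot have a compliant later repeat. All of this stands. It confines the Week 52 problem to subjects not entering the extension and to those who start it late. It does not remove the problem, because Protocol 5.1 names Week 52 and the first extension dose may be as late as Week 60.

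**A fixed cut-off is objective.** It also suits a while-on-treatment estimand. That is a fair reason to keep the date-only rule as a sensitivity analysis. It does not justify discarding a sample that the protocol asked the site to collect.

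**Flawed results will be caught.** Protocol 3.7 keeps the treatment codes unbroken for the planned analyses "until all decisions on the evaluability of the data from each individual subject have been made and documented". A reader might infer that the SAP will analyse known-bad samples, but the documents do not support that: a result voided at this review leaves the repeat as the only candidate. The selection problem arises only if the flawed result is not voided.

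**A rule may exist in unseen text.** The SAP appendices and redacted sections, such as SAP 4.1.7, could not be read. The purposes for which the readable text cites Appendices A to H do not include visit windows, but that does not prove that no rule exists.

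**PGA is an imperfect precedent.** A late PGA form still describes the visit, whereas a repeat urine collection is a new measurement. This stands, and the fix does not depend on the analogy.

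**Conclusion.** The conflict is real but minor. On the readable text, a compliant Week 52 24-hour UPCR on Days 379 to 386 is excluded from the primary analysis and replaced by imputation in CRR. The same 8-day overrun applies at every post-baseline 24-hour UPCR visit. At Week 52 it requires a visit on Day 365 or later, a repeat late enough to pass Day 378, and no extension dose yet given.

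A reader might infer that the primary result is at risk or that the arms would be affected unequally. The documents support neither: they give no repeat frequency, nothing suggests a difference between arms, and even an assumed 5% loss costs 1.7 points of power (87.9% to 86.2%) before any recovery through earlier visits. What is at stake is that the choice of the primary-endpoint value should be fixed in advance and agree with the protocol. The in-window selection problem is secondary and conditional.

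**What to change.** In SAP 4.1.1:
- Analyse a documented Protocol 5.1 repeat or delayed 24-hour UPCR at the visit it was collected for, in place of the result it replaces, even if it falls after the Table 2 window. At Week 52, do so only if it was taken before the first extension dose.
- State that confirmation samples for the Week 12, 24 and 52 discontinuation criteria, samples taken on IP discontinuation, and unscheduled samples are not replacements.
- Limit the MMRM visit levels to scheduled 24-hour UPCR visits.
- Identify replacements at blinded review, report their number by arm, and repeat the primary analysis with the date-only Table 2 rule as a sensitivity analysis.

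The cost is a few sentences, one derivation and a blinded listing of extra 24-hour UPCR samples with the reason for each. The documents do not show that the reason is recorded, so it may have to be established at that review.

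There are two drawbacks. The analysed value can be up to 8 days later than now: after a last dose on Day 337, Day 386 is 49 days later, against 41 days for Day 378. A judgement about validity also enters where the rule is now purely by date. The sensitivity analysis shows whether either matters.
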